5.1. Allocation to Treatment

Subjects will be randomized at Baseline to one of the following treatment groups, all subjects will receive SC and PO treatment during the Double-blind Treatment period of the study:

Table 4. Study Treatments

Treatment Group	Subcutaneous Investigational Product (SC)	Oral Investigational Product (PO)
1	Placebo for tanezumab once every 8 weeks x 7 doses	Celecoxib 100 mg BID through Week 56
2	Tanezumab 5 mg once every 8 weeks x 7 doses	Placebo for celecoxib through Week 56
3	Tanezumab 10 mg once every 8 weeks x 7 doses	Placebo for celecoxib through Week 56

Subjects will be randomly assigned in a 1:1:1 ratio to the above treatment regimens according to a computer generated randomization code. The randomization will not be stratified. Randomization will be coordinated centrally through IRT. The system will provide subject identification numbers at Screening, which will subsequently be linked to the treatment assignments at Randomization. The randomization code will be securely maintained by a person(s) who is independent of the trial conduct and produces the randomization code. It is the responsibility of the Principal investigator to ensure that the subject is eligible for participation in the study before requesting Randomization. The study site will obtain the subject's randomization number from the IRT. Further details will be provided in the Pharmacy Manual.

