6. STUDY PROCEDURES

Refer to Schedule of Activities ([Table 1](#) and [Table 2](#)) for the lists of procedures to be performed throughout the study.

If possible, each subject's clinic visit should be conducted at approximately the same time of day throughout their participation in the study. As a general rule, scales/instruments should be completed first by the subject upon arrival at the clinic and vital signs should be assessed prior to blood draws at non-dosing visits.

The study visit windows are ± 2 days for the visit at Week 2 and ± 3 days for the visit at Week 4. The study visit windows are ± 7 days for the clinic visits at Weeks 8, 16, 24, 32, 40, 48 and 56 and for the visits during the Follow-up Period and for the Early Termination Visits. The study visit windows are ± 7 days for the telephone visits at Weeks 12, 20, 28, 36, 44, 52, 60, 68, 72, 76 and during the Early Termination Follow-up. Study visits should be scheduled with reference to the original baseline visit date as much as possible. Subject scheduling issues should be brought to the attention of the study monitor for resolution. Dosing visits should occur no earlier than 7 weeks from the previous injection. The Week 24 X-rays may be obtained up to 30 days before the Week 24 visit, but must be completed and read by the Central Reader before the Week 24 dose of SC investigational product is administered. The visit window for the Week 56 X-rays is ± 30 days from the nominal time point of the visit. The window for the Week 80 X-rays is ± 30 days of the nominal time of the visit but should be obtained as close as possible to the Week 80 visit, and preferably no more than 14 days after the Week 80 visit.

Subjects will be reminded to abstain from taking rescue medication 24 hours prior to any study visit at which efficacy data is collected.

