9.1. Sample Size Determination

In terms of the study feasibility and the safety evaluation described below, the total sample size will be approximately 200 subjects (170-220 subjects, approximately 66 subjects [56-73 subjects] per treatment group). However, it is acceptable to randomize more than 220 subjects from the safety perspective as described below because primary objective is to evaluate the long-term safety.

Japanese subjects are enrolled in two studies within the tanezumab CLBP program (A4091059 and this study). In ongoing A4091059 study (randomization was finished in June 2017), 129 Japanese subjects were randomized and appropriately 57 Japanese CLBP subjects are expected to be initially randomized to the tanezumab arm. Considering approximately 133 (113-146) subjects are expected to be randomized to the tanezumab arm in this study, the safety data will be collected from approximately 190 (170-203) Japanese CLBP subjects treated with tanezumab.

The primary objective of this study is the evaluation of long term safety. The number of subjects who complete this study is estimated as described below. Both these protocols

require subjects to meet the efficacy response criteria (defined as at least a 30% reduction in weekly average LBPI score at week 16 relative to Baseline and at least a 15% reduction in weekly average LBPI score from Baseline at any week from week 1 to week 15) at week 16 in order to continue in the study. The proportion of 30% responders at week 16 was approximately 60% in two OA phase 3 studies (A4091011, A4091014) and approximately 42% in one CLBP phase 3 study (A4091012). On the other hand, the proportion of subjects discontinuing after week 16 is assumed to be approximately 10% for OA and approximately 20% for CLBP based on the results of discontinuation for reasons other than insufficient clinical response in these studies.

Therefore, the proportion of subjects expected to complete this study was calculated as approximately 54% ($=100*0.6*0.9$) based on the two OA studies and approximately 34% ($=100*0.42*0.8$) based on the CLBP study, and the proportion of completers of this study is estimated to be between 34% and 54%. Table 6 shows the relationship between the proportion of completers and the number of subjects with one year exposure.

From Table 6, if the proportion of completers is at least 43% in the CLBP program, approaching 100 subjects are expected to be treated with tanezumab for a minimum of one year.

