As for LBPI and RMDQ, ANCOVA with covariates described in [Section 5.2.2](#) will be conducted for all time points up to week 56. Study site will be fitted as a random effect in the ANCOVA model. This analysis will use multiple imputation for missing data as described above. While the table describes the multiple imputation strategy specific for the Week 16 time point, it also applies to all other analysis time points, eg, ‘Week 2’ would be substituted for ‘Week 16’ in the above table, to describe the Week 2 multiple imputation strategy.

The responder endpoints will be summarized, using both BOCF and LOCF for missing data of the response endpoint at a particular time point. Imputation using BOCF will lead to the subject being assessed as a non-responder. In addition, a mixed BOCF/LOCF imputation for response endpoints will be used. In this analysis BOCF imputation (ie, a subject would be a non-responder) would be used for missing data due to discontinuation for reasons of lack of efficacy, patient's not meeting protocol-specified pain criteria, adverse event or death up to the time point of interest, and LOCF imputation would be used for missing data for any other reason.

Note, if Baseline is missing then the subject data for the change from Baseline will be set to missing for all efficacy analyses for that parameter. A subject who has a missing Baseline score will be missing for the response criteria for endpoints where the response is based on one parameter.

The CLBP-RI (Chronic Low Back Pain Responder Index) is based on 3 parameters (aLBPI, RMDQ and PGA-LBP). It is set to missing if any one out of these three parameters are missing at baseline or for the relevant post-Baseline timepoint (per its definition, a response can still be achieved if all three component parameters meet certain criteria).

For the RMDQ, any missing items are treated as the patient not having that symptom, and so not included in the RMDQ total score.

The BPI-sf Pain interference index score is calculated from the seven BPI-sf pain interference items. The composite index score is calculated as the mean of the non-missing items as long as ≥ 4 of the 7 items are non-missing, otherwise (≤ 3 items non-missing) the index score is missing.

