6.2. Secondary Endpoints

All analyses in this section use the ITT analysis set, if not otherwise specified. If not otherwise specified, the observed data (no imputation for missing data) will be summarized.

All efficacy assessments during the treatment period are made on the analysis windows defined in [Appendix 2.1](#). Using these windows we find the analysis window for a patient's last subcutaneous (SC) dose. Any data included in a window that is up to 8 weeks from this last SC dose window is 'on-treatment', and any data included in a window that is more than 8 weeks after the last SC dose window is off-treatment. Data in on-treatment analysis windows will be used in summaries and analyses, while data in off-treatment analysis windows will be excluded from all summaries and analyses of treatment period efficacy data, ie, up to Week 56.

Efficacy data collected via subject diary (aLBPI and rescue medication use) are collected daily or weekly, not at study visits. Diary efficacy data will be considered on-treatment if it is collected up to 84 calendar days after the last SC dose. Diary efficacy data collected more than 84 calendar days after the last SC dose will be considered off-treatment and excluded from summaries and analyses of treatment period efficacy data.

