6.2.1. Average Low Back Pain Intensity (LBPI) Score

Change from Baseline to Weeks 1, 2, 4, 8, 12, 16, 24, 32, 40, 48, 56 and 64 in average LBPI score.

For each treatment and each timepoint assessed, the endpoint will be summarized along with 95% CIs. Handling of missing data is described in [Section 5.3](#).

The ANCOVA model for change from baseline of aLBPI up to week 56 described in [section 5.2.2](#) will also be conducted. The plot of LS mean (+/- SE) for change from baseline up to week 56 will also be prepared.

LBPI data obtained after the early termination visit and considered as off-treatment will be shown in the listing and not be included in any summaries and analyses.

Cumulative distribution of percent change from Baseline in average LBPI score to Weeks 16, 24 and 56.

The cumulative aLBPI response at Weeks 16, 24 and 56 using response definitions from a reduction of >0% to =100% (in steps of 10%) will be summarized, using observed data, mixed BOCF/LOCF, and also LOCF and BOCF imputation for aLBPI (see [Section 5.3](#)).

Imputation with BOCF for subjects with missing data at that timepoint will lead to the subjects being assessed as non-responders for the response endpoint.

Plots of cumulative distribution of percent change from Baseline in average LBPI score to Week 16 and Week 56 (mixed BOCF/LOCF) will be created.

Response as defined by a $\geq 30\%$, $\geq 50\%$, $\geq 70\%$ and a $\geq 90\%$ reduction from Baseline in weekly average LBPI score derived from the subject diary at Weeks 16, 24, 40 and 56.

For each treatment and each timepoint assessed, the number and percentage of subjects in each response category endpoint will be summarized along with 95% CIs. Treatment differences of proportion of responder between each tanezumab treatment group versus celecoxib group will be estimated with 95% CI of Agresti-Caffo method. These analyses use observed data, mixed BOCF/LOCF, and BOCF and LOCF for missing data. The use of BOCF for missing data implies subjects with missing data are included in the analysis as non-responders. Similarly the use of LOCF in the case where subjects have no post-Baseline data (and Baseline would be carried forward) again implies those subjects are included in the analysis as non-responders.

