EQ-5D-5L is collected at Baseline, Weeks 16 and 56, and ET1. WPAI:LBP is collected at Baseline, Weeks 16, 56, 64, and ET1 and ET2. HCRU is collected at Baseline, Weeks 64 and 80, and ET2 and ET3. TSQM and mPRTI are collected at Weeks 16 and 56, and ET1. The visit window for these visits will be defined below.

EQ-5D-5L, TSQM, mPRTI

| Visit | Target Study Day | Window |
|----------|---|-----------------------|
| Baseline | 1 (defined as initial day of study drug administration) | [-7, 1] |
| Week 16 | 113 | [2, 253] |
| Week 56 | 393 | [254, no upper limit] |

HCRU

| Visit | Target Study Day | Window |
|----------|---|-----------------------|
| Baseline | 1 (defined as initial day of study drug administration) | [no lower limit, 1] |
| Week 64 | 449 | [2,505] |
| Week 80 | 561 | [506, no upper limit] |

WPAI: OA,

| Visit | Target Study Day | Window |
|----------|---|-----------------------|
| Baseline | 1 (defined as initial day of study drug administration) | [no lower limit, 1] |
| Week 16 | 113 | [2,253] |
| Week 56 | 393 | [254, 421] |
| Week 64 | 449 | [422, no upper limit] |

Data in on-treatment analysis windows will be used in summaries and analyses of treatment period efficacy data, ie, up to Week 56, while data in off-treatment analysis windows will be only included in summaries (at Week 64, Week 80, 16 Weeks after Last Dose, and End of Study). Data in off-treatment analysis windows will be imputed, if needed, in analyses.

Any data collected up to 8 weeks (per the windowing rule above) from the last SC dose window is ‘on-treatment’, and any data collected more than 8 weeks (per the windowing rule above) after the last SC dose window is off treatment. For example, for patients whose last SC dose is at Week 8 (per the windowing rule above), any data collected after Week 16 (per the windowing rule above) will be off-treatment.

For the weekly diary average Low Back Pain Intensity scores, the data will be allocated to study weeks based on calendar weeks relative to the baseline visit (study day 1) and not based on the post-baseline visit schedule. The table below describes the visit days for each week. The mean of available weekly data in each of the weekly intervals will be used to calculate the weekly diary average Low Back Pain Intensity scores.

| Study Week | Days |
|------------|---------|
| 1 | 1-7 |
| 2 | 8-14 |
| 3 | 15-21 |
| 4 | 22-28 |
| 5 | 29-35 |
| 6 | 36-42 |
| 7 | 43-49 |
| 8 | 50-56 |
| 9 | 57-63 |
| 10 | 64-70 |
| 11 | 71-77 |

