“16 Weeks after Last Dose”. This window will include the average of all data collected from 13 to 16 calendar weeks (85 to 112 calendar days) past the date of the last SC dose. All available on- or off-treatment data will be used for this window after the planned treatment period.

Note that, similar to data collected at clinic visit, any data collected via diary up to 84 calendar day (12 weeks, 8 weeks + a 4 week window) from the date of the last SC dose are ‘on-treatment’, and any data collected more than 84 calendar day (12 weeks, 8 weeks + a 4 week window) from the date of the last SC dose are off treatment.

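### The 84-day diary limit does not match the clinic on-treatment rule: read literally, a subject stopped as a Week 16 non-responder can supply an observed Week 24 pain score, and SAP 6.2.1 leaves unclear whether that is intended

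*SAP*

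**What the plan says.** On-treatment status for efficacy data is set by the last subcutaneous (SC) dose in every arm (SAP Section 6.2 and Appendix 2.1).

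- **Clinic data.** Windows more than 8 weeks after the last SC dose window are off-treatment. Appendix 2.1 gives an example: "for patients whose last SC dose is at Week 8 (per the windowing rule above), any data collected after Week 16" will be off-treatment. The clinic Week 16 window is Days 86-141.
- **Diary data** (low back pain intensity, LBPI, and rescue use). Section 6.2: "Diary efficacy data will be considered on-treatment if it is collected up to 84 calendar days after the last SC dose". Appendix 2.1 repeats the limit as "similar to data collected at clinic visit, any data collected via diary up to 84 calendar day" and explains it as 8 weeks plus a 4-week window. The diary Week 24 window is Days 141-168, and its score is the mean of whatever entries are available.
- **After early termination.** Section 6.2.1: "LBPI data obtained after the early termination visit and considered as off-treatment will be shown in the listing" and left out of summaries and analyses.
- **Imputation.** Section 5.3 imputes baseline-like values when data are missing after discontinuation for insufficient response or the pain criteria. For the responder endpoints' mixed method, "BOCF imputation (ie, a subject would be a non-responder) would be used for missing data due to discontinuation for reasons of lack of efficacy", with the protocol pain criteria also named.

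Under the protocol, Week 16 non-responders leave treatment (Sections 3 and 6.4.5) but keep the weekly LBPI diary to Early Termination Visit 2 (Section 7.1.1). In the celecoxib arm the injection is "Placebo for tanezumab once every 8 weeks x 7 doses" (Section 5.1, Table 4).

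**The concern.** Section 5.3 explains that a poor value is imputed for subjects who stop for a poor outcome. Failing the Week 16 response rule is the most foreseeable such reason. If the diary rule lets one later entry count as the Week 24 value, Week 24 is no longer missing and the imputation never applies. An invented illustration: Baseline 5 and a Week 16 score of 4 is a 20% reduction, so the subject is stopped; a Day 141 entry of 3 is a 40% reduction and would count as a 30% responder at Week 24.

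At stake are the Week 24 tanezumab-versus-celecoxib contrasts in average LBPI: the analysis of covariance difference and the responder differences.

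A second, separate matter concerns the celecoxib arm. Because its injection is placebo, an SC-based limit does not mark the end of active treatment there. The plan does not say that scores after the last capsule are included.

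**Working it through.** **1. The plan's own figure.** 8 x 7 + 4 x 7 = 84 days. It reproduces.

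**2. Where the limit falls.** The diary Week 24 window opens on 20 x 7 + 1 = Day 141. Protocol Section 6 allows a window of plus or minus 7 "days for the clinic visits at Weeks 8, 16, 24, 32, 40, 48 and 56", so the Week 8 dose can fall on Days 50-64. Limit = dose day + 84. Overlap with Week 24 = max(0, limit - 140). The SAP does not say whether the dose day counts as day 1; if it does, the limit is dose day + 83.

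| Week 8 dose | Limit (+84) | Overlap | Limit (+83) | Overlap |
|---|---|---|---|---|
| Day 50 | 134 | 0 | 133 | 0 |
| Day 56 | 140 | 0 | 139 | 0 |
| Day 57 | 141 | 1 day | 140 | 0 |
| Day 64 | 148 | 8 days | 147 | 7 days |

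Day 141 is therefore the last day of Week 16 in the clinic table and the first day of Week 24 in the diary table. Protocol Section 9.3 uses 10 weeks (70 days) for Early Termination visit data. That would give Days 127 and 134 for doses on Days 57 and 64, with no overlap, but it is not written for the diary.

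**3. How many subjects.** Protocol Section 9.1 takes Week 16 30% response as "approximately 60% in two OA phase 3 studies (A4091011, A4091014) and approximately 42% in one CLBP phase 3 study". Treating everyone else as a Week 16 stopper gives 66 x 0.40 = 26.4 to 66 x 0.58 = 38.3 per arm of 66. This is an upper bound, because it includes earlier stoppers. A subject dosed only on Day 1 has a limit of Day 85 and cannot reach Week 24.

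Assume Week 8 doses spread evenly over Days 50-64, one entry a week on an evenly spread weekday, and full diary compliance. The chance of an entry in the overlap is min(1, overlap/7).

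- +84 convention: [(1+2+...+7)/7 + 1]/15 = 5/15 = 0.333.
- +83 convention: [(1+2+...+7)/7]/15 = 4/15 = 0.267.
- Subjects: 26.4 x 0.267 = 7.0 to 38.3 x 0.333 = 12.8, or about 7-13 of 66 per arm.
- Every dose on Day 57: 26.4/7 = 3.8 to 38.3/7 = 5.5 under +84, and none under +83.
- Every dose by Day 56: none.

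Each such subject who records a response moves that arm's Week 24 responder proportion by 1/66 = 1.5 percentage points.

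**4. Later visits.** 113 + 84 = 197, 169 + 84 = 253, 225 + 84 = 309 and 281 + 84 = 365 are the first days of the diary windows for Weeks 32, 40, 48 and 56. Section 9.1's post-Week 16 discontinuation rates give 66 x 0.60 x 0.10 = 4.0 to 66 x 0.42 x 0.20 = 5.5 stoppers per arm. Over five dosing intervals that is 0.8-1.1 each. Multiplied by 1/7 to 1/3, it is about 0.1-0.4 subject per arm per visit.

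**5. Celecoxib arm.** With a last injection on Day 57 and, for illustration, capsules stopped on Day 113, Days 114-141 (28 days) still count as on-treatment diary time. Section 5.3 acts only on missing values, so it does not reach these scores.

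**The case against.** **Section 6.2.1 may already exclude these scores.** Its sentence can be read as saying that LBPI after the early termination visit is regarded as off-treatment. The SAP's change history describes the addition simply as handling of LBPI after that visit. Early Termination Visit 1 is 8 weeks after the last SC dose, about Day 113 for these subjects, so entries on Days 141-148 would then drop out. This is a fair reading and it stands as a real alternative. The literal wording, however, joins two conditions, after the visit and off-treatment, and Section 6.2 makes Day 141 on-treatment. Nor does the sentence say which of the three Early Termination visits it means.

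**The general window rule already makes Week 24 off-treatment.** Section 6.2 opens with a rule for all efficacy assessments, and the Appendix 2.1 example says any data. But Section 6.2 then separates diary data from visit data and gives them their own limit. The SAP does not say which rule governs.

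**The overlap is trivial.** On schedule it is one day, or none if the dose day is day 1, and Protocol Section 6 asks sites to keep visits close to the baseline-based schedule. This stands, and it is why no single expected count should be quoted.

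**The celecoxib point is an estimand choice.** Protocol Section 9.3 admits Early Termination visit data within 10 weeks of the last dose with no oral-dose condition, and one SC-based limit treats all arms of a double-dummy trial alike. This largely stands. What remains is disclosure.

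**Conclusion.** The diary and clinic rules disagree at the Week 24 boundary, and Section 6.2.1 does not settle which result is intended. On the literal reading, a stopped Week 16 non-responder can be counted as observed at Week 24 from one entry. On the alternative reading of Section 6.2.1, this largely disappears.

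A reader might infer more than the documents support:

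- **That the SAP definitely counts non-responders at Week 24.** It does so under one of two tenable readings.
- **That 7-13 of 66 per arm is a forecast.** It is an upper-bound illustration resting on assumed dosing and diary days, and it does not estimate how many subjects would change responder status. The range starts at none.
- **That the rule favours one arm.** Direction is unknown. The rule is the same in all arms, the displaced value is baseline-like, Baseline itself is measured on stabilised celecoxib (Protocol Section 4.3), and scores after stopping are not in the documents.
- **That the SC-based limit is an error in the celecoxib arm.** It is a defensible choice that should be stated.

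The effect at Weeks 32-56 is small. The endpoints are secondary and no hypotheses are tested (SAP Section 5.1), so severity is minor to moderate.

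**What to change.** 1. **Align the diary rule.** State that diary data from a subject not dosed at a visit do not count toward the next reported window after that interval, for example Week 24 when there was no Week 16 dose. Week 24 is then missing and handled under Section 5.3. Cost: one line in a derivation.
2. **Reconcile the text.** Make the 84-day limit in Section 6.2 and Appendix 2.1 consistent with Section 6.2.1 and the Appendix 2.1 example. Name the early termination visit meant in Section 6.2.1 and say whether the dose day is day 0 or day 1. Cost: wording only.
3. **Disclose the celecoxib point.** State that the SC-based limit, like the 10-week allowance in Protocol Section 9.3, admits scores after oral discontinuation, and tabulate those scores by arm and visit. Oral dosing is on the case report form (Protocol Section 5.3). Where the last-capsule date is missing, the discontinuation time already derived for SAP Section 6.2.8 can stand in. Cost: one derivation and one table.
4. **Optional.** A labelled sensitivity analysis that treats celecoxib-arm scores after the last oral dose as missing. It uses different cut-offs by arm and adds imputation in the celecoxib arm, so it should not replace the main analysis.
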